2 STUDY OBJECTIVES

2.1 Primary Objectives

- To compare pre-treatment (Day 3) to end of treatment (Day 8) 24-hour CGM glucose for single and multiple doses of ORMD-0801 vs placebo.
- To evaluate safety parameters for single and multiple doses of ORMD-0801 vs placebo.

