1.2. Study Overview

This a phase 2a, randomized, double-blind, double-dummy, placebo-controlled, 3-way crossover study enrolling approximately 30 adult subjects with T2DM from age 20 to 75 inclusive. Following a 7-10 day Screening period, eligible subjects will be housed in the CRU for the duration of each treatment cycle beginning with a 3-day single-blind placebo run-in. On Day 4, each subject will be randomized to a treatment sequence that will include three treatment assignments for each of three treatment periods according to the randomization scheme.

All eligible subjects will receive placebo plus two of the following: ORMD-0801 460 IU qd, OMRD-0801 bid, or ORMD-0801 tid. Subjects will receive the randomized treatment from Day 4 through Day 8. A 24-hour single-blind placebo washout will be done on Day 9. Subjects will be discharged on the morning of day 10. Each treatment Period will be separated by a 2-week washout. A final follow-up visit will be performed 1 week after the end of the third treatment period.

In addition, adverse events, clinical laboratory values, vital signs, and electrocardiograms (ECGs) will be evaluated periodically for safety.

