1.3. Study Objectives

1.3.1 Primary Objectives

The primary objectives of this study are to compare pre-treatment (Day 3) to end of treatment (Day 8) 24-hour CGM glucose for single and multiple doses of ORMD-0801 vs placebo and to evaluate safety parameters for single and multiple dose of ORMD-0801 vs placebo.

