2.1. General Statistical Methods

All measured variables and derived parameters will be listed individually and, if appropriate, tabulated by descriptive statistics. For descriptive statistics summary tables will include by study group summaries of sample size, arithmetic mean, standard deviation, coefficient of variation (if appropriate), median (and other percentiles, if appropriate), minimum and maximum values, and 95% Confidence Intervals (if appropriate). For categorical variables summary tables will include by study group summaries of frequency counts

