2.8. Efficacy Evaluations

2.8.1. Continuous Glucose Monitoring

The last 2 days with at least 80% of expected measurements prior to dosing will be considered the run-in days for each of the parameters. The last 2 days with at least 80% of expected measurements prior to 8 hours after the last dose will be considered the on treatment days. The measurements more than 8 hours after the last dose will be considered the follow-up days.

The 24-hr period (6AM to 6AM), nighttime (from 10pm to 6am), daytime (6AM to 10PM), and post-prandial (first hour after meal start time including breakfast, lunch, and dinner) glucose values will be summarized. The mean, standard deviation, minimum, maximum, first quartile, median, third quartile and inner-quartile range will be presented.

The area under the curve (AUC) will be derived for each of the time periods (24-hour, daytime and nighttime) using the indicated days (run-in days, treatment days and follow-up days). The average glucose measurement will be derived by dividing the AUC by the number of observed hours. The average change from run-in will be derived for each treatment regimen for both the treatment days and the follow-up days.

The placebo adjusted change in means will be derived for each of the active therapy regimens by subtracting the placebo mean (the mean change from run-in while the subject was receiving placebo) from the active therapy mean (the mean change from run-in while the subject was receiving the active therapy).

The placebo adjusted change in means will be derived for both the treatment days and the follow-up days. The placebo adjusted change in means will be analyzed using an Analysis of Variance (ANOVA) with treatment as the main effect to determine whether multiple doses a day has an effect on the CGM parameters. If the residuals are not normally distributed, then a Kruskal-Wallis test (one-way analysis of variance on the ranks) will be performed.

The ratios of the placebo adjusted change in means between the active treatments within each subject will also be derived to estimate the magnitude of the dose response.

Summary statistics will be presented for both the placebo adjusted change in means and the ratios of the placebo adjusted change in means. Analysis results will be presented for the change in means.

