2.10. Other Analyses

No other analyses are planned at this time.

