2.11. Sample Size and Power Considerations

A total of 30 subjects will be randomized to receive either placebo, ORMD-0801 460 IU qd, ORMD-0801 460 IU bid, or ORMD-0801 460 IU tid during each treatment period.

This study is not powered for statistical significance.

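### The only planned CGM test compares the three ORMD-0801 regimens with each other; no test or confidence interval against placebo, the primary CGM question, is committed to

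*SAP*

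**What the plan says.** SAP 1.3.1 sets the primary CGM objective as to "compare pre-treatment (Day 3) to end of treatment (Day 8) 24-hour CGM glucose for single and multiple doses of ORMD-0801 vs placebo"; Protocol 2.1 says the same. The design gives every subject a placebo period: "All eligible subjects will receive placebo plus two of the following" active regimens (SAP 1.2).

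SAP 2.8.1 and Protocol 8.3 derive, for each active regimen, the subject's mean change from run-in on that regimen minus the same subject's mean change on placebo. Then "The placebo adjusted change in means will be analyzed using an Analysis of Variance (ANOVA) with treatment as the main effect", the stated purpose being to learn whether giving several doses a day matters. If residuals are not normal, "then a Kruskal-Wallis test (one-way analysis of variance on the ranks) will be performed" (SAP only). The placebo-adjusted changes and their within-subject ratios between regimens receive summary statistics.

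On intervals, SAP 2.1 lists "95% Confidence Intervals (if appropriate" among the general descriptive statistics. The statistics that SAP 2.8.1 lists for the glucose values include no interval. SAP 2.10 adds: "No other analyses are planned at this time". SAP 2.11 states: "This study is not powered for statistical significance".

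**The concern.** Subtracting placebo removes it as a level of the treatment factor. What remains is a three-group comparison of qd, bid and tid, and that asks about dosing frequency, not about drug against placebo. If the three regimens lower glucose equally, the one named test will show nothing however large the effect, and a non-significant result could be misread as no effect. The report would then have no prespecified inference on its primary CGM question, and any placebo interval or test added later would be post hoc.

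There is a second, smaller point. A subject's two placebo-adjusted values share one placebo value and are therefore correlated. The plan names no subject or period term, and its fallback is a one-way rank test. That the values would be treated as independent is an inference from this, not something the plan states.

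**Working it through.** **Inputs.** From the documents: 30 subjects; each receives placebo and two of three active regimens, giving 60 placebo-adjusted values. Assumed, because the documents give no SD, effect size or allocation: 10 subjects per active pair (20 values per regimen), near-balanced order, equal variance s² of the change from run-in in each period, independent periods, normality, no carryover, two-sided 5%. The plan states no power figure, so there is none to reproduce.

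**1. The planned test ignores a common effect.** With d_ik the adjusted value of subject i on regimen k, m_k the regimen mean and m the overall mean,

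F = [Σ 20(m_k − m)² / 2] / [ΣΣ(d_ik − m_k)² / 57].

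Adding a constant c to every d_ik moves m_k and m by c, and both sums are unchanged. Ranks are unchanged too. On one simulated data set, shifts of 0, −10 and −50 units gave ANOVA p = 0.292 each time and Kruskal-Wallis p = 0.351 each time.

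**2. Rejection rates when all regimens have the same true effect against placebo.** The planned F and the within-subject model used 10,000 simulated trials per scenario; the one-sample t test used 5,000.

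| Common effect | Planned one-way F | One-sample t on one regimen's adjusted values | Within-subject model, one regimen vs placebo |
|---|---|---|---|
| 0 | 1.8% | about 5% | – |
| 0.5s | 1.8% | 33% | 38% |
| 1s | 2.0% | 85% | 91% |
| 2s | 2.0% | about 100% | >99% |

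The data can answer the primary question, but the planned test does not ask it.

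**3. Precision available against placebo.**

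- Paired values: each adjusted value has variance v = 2s², so a regimen mean has variance 2s²/20 = 0.10s². The 95% half-width is t(19) × √0.10 s = 2.093 × 0.316s = 0.66s. This SE is unbiased. In terms of the SD of the adjusted change the half-width is 2.093/√20 = 0.468 SD; for assumed SDs of 15, 20, 30 and 40 mg/dL it is 7.0, 9.4, 14.0 and 18.7 mg/dL.
- Four-level model with subject fixed, before period terms: the information matrix for the three regimen-minus-placebo contrasts has diagonal 20 − 20/3 = 13.33 and off-diagonal −10/3 = −3.33 (in units of 1/s²). Its inverse has diagonal 0.09s² and off-diagonal 0.03s², so the contrasts correlate 0.33, and regimen-versus-regimen variance is 2(0.09 − 0.03)s² = 0.12s². Adding period terms raises the first to 0.091s²; residual df = 90 − 30 − 2 − 3 = 55; half-width about 0.60s.

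**4. Secondary point: regimen against regimen.** Under independence the variance of a difference is 2v/20 = 0.20s². Ten subjects contribute to both regimens, with correlation ρ between their two values, so the true variance is 2v/20 − 2 × 10ρv/400. At ρ = 0.5, which independent periods imply, this is 0.20s² − 0.05s² = 0.15s². The SE ratio is √(0.20/0.15) = 1.15; for ρ = 0, 0.3, 0.5 and 0.7 it is 1.00, 1.08, 1.15 and 1.24. The error is conservative: true size is about 2% instead of 5%. For effects of 0, 0.5s and 1s on qd, bid and tid, power is about 47% one-way and about 71% with subject and period terms.

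**5. Multiplicity of the proposed output.** With three unadjusted 95% CIs and contrast correlation 0.33, the chance that at least one excludes zero when no regimen works is about 13% (1,000,000 draws, 57 df, no period terms).

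**The case against.** The best defence is that the placebo comparison is planned, as estimation. The plan derives the active-minus-placebo change for each regimen and summarises it, and with n, mean and SD a reader can form the paired interval. The objective says compare, not test, and the study is openly unpowered. The ANOVA fits its own stated purpose. SAP 2.1 permits intervals, the closing sentence of SAP 2.8.1 about results for the change in means is ambiguous, and the table shells, held in a separate file, might include one. An interval on the paired values would close most of the gap (0.66s against 0.60s).

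Much of this stands. The contrast is described, a paired interval would be an acceptable minimum, and being unpowered is a good reason to prefer estimation. But a conditional, general clause does not commit to an interval on the primary contrast, and the only analysis named is the one on adjusted values. Elsewhere the SAP does name between-treatment comparisons: ANOVA on changes in laboratory values and vital signs, and Fisher's LSD for the PK/PD areas. The primary CGM endpoint has no such comparison with placebo.

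Two numerical objections are also fair. First, the 2% rejection rates depend on reading the ANOVA as one-way. With a subject term, the test on adjusted values rejects 4.9% under the null, 4.8% at a common effect of 1s, and 65% for the 0/0.5s/1s gradient. That restores the nominal size but leaves the test just as blind to a common effect. Second, exactly equal effects are the extreme case. Yet with effects of 0.33s, 0.67s and 1s the one-way F rejects in 20% of trials, while the one-sample test against placebo rejects in 17%, 52% and 85% for qd, bid and tid. The mismatch is therefore not confined to the extreme case.

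**Conclusion.** The concern holds. Followed as written, the plan gives inference on dosing frequency and none on its primary CGM objective. That the test cannot respond to a shared effect is exact algebra and needs no assumption about SD, allocation or correlation. The sizes (about 2% rejection against 38%, 91% and more than 99%; half-widths of 0.66s and 0.60s) rest on the assumed balanced allocation, equal variances, independent periods and no carryover, and the 2% also on the one-way reading. The model figures take subject as fixed; the blindness of the planned test does not depend on that choice.

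The shared-placebo point is secondary and conditional. It creates no false positives and costs only precision and power when regimens are compared. The table shells were not available for this review; an interval there would help, but the method belongs in SAP 2.8.1.

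**What to change.** In SAP 2.8.1 and Protocol 8.3:

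- Analyse the change from run-in in every period, placebo included, with a linear mixed model: treatment (placebo, qd, bid, tid) and period as fixed effects, subject as random.
- Make each regimen minus placebo, with its 95% CI, the primary CGM output. Describe it as estimation without multiplicity control, given the unpowered design, and state the roughly 13% chance that at least one interval excludes zero when no regimen works.
- Keep regimen-versus-regimen contrasts from the same model as secondary.
- Replace the residual-triggered switch to Kruskal-Wallis with a sensitivity analysis that keeps the within-subject structure.

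This covers CGM only. Protocol 5.2 ties the time of day of PK/PD sampling to the regimen, so those comparisons need their own within-subject method.

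Cost: revised SAP and protocol wording and a few lines of code. No new data, visits or subjects.

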
Summary of Assessments
	
Safety will be verified by monitoring adverse events, clinical laboratory values, vital signs, physical examinations, and ECG.
 
CGM Monitoring will be used throughout the entire treatment period to compare pre-treatment, treatment, and post-treatment glucose levels, as well as post-prandial glucose.
 
Pharmacokinetics/Pharmacodynamics will be used to compare pre-treatment and post-treatment C-peptide and insulin levels.

Duration of Participation
	
Subjects will be evaluated for participation in the study during a 7-10 day Screening period. The planned length of participation is about 65 days (from Visit 2 through Visit 3). During each Visit 2 treatment Period, the subjects will be confined to the unit for 8 nights from check-in on the evening of Day 2 through completion of the post-treatment procedures on the morning of Day 10.

Subject Selection Criteria
	
This study will enroll T2DM subjects with an HbA_{1c} $\geq 7.5\%$ and $\leq 10.5\%$, who are taking metformin only, metformin in addition to sulfonylurea, metformin in addition to TZD, metformin in addition to an SGLT-2 inhibitor, or metformin in addition to a DPP-4 inhibitor with all treatment regimens stable for a minimum of 8 weeks prior to Visit 2/Period 1/Day 1.

Statistical Methods
	
Pharmacokinetics/Pharmacodynamics (PK/PD) The PK/PD analysis will be conducted using model-independent methods and will be based on plasma concentrations of insulin and C-peptide.
 
Continuous Glucose Monitoring The placebo adjusted change in means will be analyzed using an Analysis of Variance (ANOVA) with treatment as the main effect to

	
determine whether multiple doses a day has an effect on the CGM parameters.
 
The ratios of the placebo adjusted change in means between the active treatments within each subject will also be derived to estimate the magnitude of the dose response.
 
Summary statistics will be presented for both the placebo adjusted change in means and the ratios of the placebo adjusted change in means. Analysis results will be presented for the change in means.
 
Safety All safety parameters will be summarized and listed using descriptive statistics.

--	--

Table of Contents

TITLE PAGE	1
SPONSOR PROTOCOL APPROVAL SIGNATURE PAGE	2
INVESTIGATOR SIGNATURE PAGE	3
SYNOPSIS.....	4
LIST OF ABBREVIATIONS AND DEFINITIONS OF TERMS.....	11
1 INTRODUCTION	13
2 STUDY OBJECTIVES.....	15

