8.4.8 Handling of Missing, Unused, or Spurious Data

Descriptive statistics and listings will be provided for all data. No substitution of missing data will be used in any calculations. Data points that appear to be spurious will be investigated and will not be excluded from the listings. Influential cases will be handled in an appropriate statistical manner.

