2.13. Handling Missing Data

Listings will be provided for all data. Descriptive statistics will be provided for all planned visits as provided on the Case Report Forms (CRFs).

Study days will be analyzed using the study days as reported in the Case Report Form. Likewise, unscheduled visits will not be reassigned a visit number based on the visit date.

Dates related to the adverse events and medications will be imputed using the rules below in an effort to categorize them properly into the summary tables.

Imputing partial or missing start dates:

- If the year is unknown, then the start date will not be imputed. The date will remain missing.
- If the month is unknown and the year is the same as the first dose date of the study, then impute the month and day of the date to be equal to the first dose month and day. Otherwise, impute the month as January.
- If the day is unknown and the month and year are the same as the first dose date of the study, then impute the day to be equal to the day of the first dose. Otherwise, impute the day as '01'.

Impute partial or missing stop dates:

- If the year is unknown, then the stop date will not be imputed. The date will remain missing.
- If the month is unknown, impute the month as December.
- If the day is unknown, impute the day to be the last day of the month.

If an imputed stop date is greater than the date of study completion/discontinuation date of the study, then the imputed stop date will be set equal to the date of completion/discontinuation date.

The imputed dates will be stored in the analysis datasets along with the original dates as recorded by the sites.

Efficacy analyses will be performed for the ITT population in which CGM data was collected during treatment. The weighted mean night time glucose levels will be calculated on CGM data as described in Section 2.8.1. No imputation will be used other than application of linear interpolation for calculation of the trapezoidal areas.

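### The dose-response magnitude rests on individual ratios whose denominators can be near zero or of either sign, so their mean and SD are unreliable unless the effect is large

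*SAP*

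**What the plan says.** SAP 2.8.1 first forms a placebo-adjusted change for each active regimen "by subtracting the placebo mean (the mean change from run-in while the subject was receiving placebo) from the active therapy mean". It then adds, on dose response: "The ratios of the placebo adjusted change in means between the active treatments within each subject will also be derived to estimate the magnitude". Protocol 8.3 has the same text. The Protocol Synopsis, under Statistical Methods, commits to reporting the result: "Summary statistics will be presented for both the placebo adjusted change in means and the ratios of the placebo adjusted change in means".

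SAP 2.1 says what summary statistics are: "For descriptive statistics summary tables will include by study group summaries of sample size, arithmetic mean, standard deviation, coefficient of variation (if appropriate), median", followed by the minimum, the maximum and, where appropriate, a 95% CI.

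No formal analysis is attached to the ratios: "Analysis results will be presented for the change in means".

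Two passages might have supplied a safeguard. Protocol 8.4.8, within the safety evaluation, says "Influential cases will be handled in an appropriate statistical manner". SAP 2.13 says "No imputation will be used other than application of linear interpolation for calculation of the trapezoidal areas". Neither addresses a ratio with a small or wrong-sign denominator, and the text does not say which regimen is the denominator.

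**The concern.** The denominator is a difference between two noisy changes in the same subject. Nothing keeps it away from zero or fixes its sign. One denominator close to zero produces a very large ratio, positive or negative, which then dominates a mean and SD taken over about 10 subjects. A negative ratio has no dose-response meaning. A positive ratio formed from two wrong-sign effects looks sensible but has none either.

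The same placebo value also enters numerator and denominator, so the two move together even when the drug does nothing. At small effects this pulls the typical ratio toward 0.5, whatever the truth.

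This is the quantity the plan labels as estimating the magnitude of dose response. If effects are modest relative to their variability, it can be reported with the wrong size or the wrong sign.

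**Working it through.** **Inputs from the documents.** 30 subjects (SAP 2.11). Each receives placebo plus two of three active regimens (SAP 1.2), so each gives one ratio, for one of three pairs. No effect size, SD or power is stated, and SAP 2.11 says the study is not powered. There is therefore no plan figure to reproduce.

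**Assumptions.** Period changes are independent and normal with SD s. Subjects split equally, 30/3 = 10 per pair (the randomization plan is a separate document). Effects are expressed in units of s.

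**Step 1: wrong-sign denominators.** The denominator A - P has SD s√2, so P(wrong sign) = Φ(-effect/(s√2)). For 10 subjects, P(at least one) = 1 - (1 - p)^10.

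| Effect | p, one subject | At least one of 10 |
|---|---|---|
| 1s | 0.24 | 94% |
| 2s | 0.079 | 56% |
| 3s | 0.017 | 16% |
| 4s | 0.002 | 2% |

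**Step 2: the planned mean and SD.** Ratio = (B - P)/(A - P), true ratio 1, 10 subjects, 100,000 simulated trials per row.

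| Each effect | Mean ratio, 5th to 95th percentile | Mean ratio negative | SD of ratios, median (5th to 95th) |
|---|---|---|---|
| 1s | -3.8 to 5.4 | 25% | 2.7 (0.8 to 29) |
| 2s | -1.6 to 3.7 | 12% | 1.5 (0.5 to 17) |
| 3s | 0.3 to 2.2 | 4% | 0.7 (0.3 to 6.0) |
| 4s | 0.8 to 1.5 | 1% | 0.4 (0.2 to 1.5) |

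More subjects do not help. At 1s the range is -3.9 to 5.4 with 8 per pair and -3.9 to 5.3 with 12. Under normality this ratio has no finite mean, so averaging does not settle it.

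**Step 3: the planned median.** It is steadier but biased at small effects.
- True ratio 1: it centres at 0.69 (1s/1s), 0.91 (2s/2s) and 0.99 (3s/3s).
- True ratio 2 with the smaller effect (1s) as denominator: it centres at 1.15.
- True ratio 0.5 with the larger effect (2s) as denominator: it centres at 0.50 (0.11 to 0.89).
- No effect at all: it centres at 0.5, because of the shared placebo value.

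The bias therefore depends on the true ratio and on the direction chosen.

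**Step 4: the alternative.** Fit subject, period and treatment to all periods. Ignoring the small loss from period imbalance, each active regimen is given to 20 subjects and each pair of actives shares 10. The information for an active contrast is 20 × 2/3 + 10/3 = 50/3. The variance of a difference is 2s²/(50/3) = 0.12s², so SE ≈ 0.346s; with period fitted it is 0.347s. Residual df = 90 - 30 - 2 - 3 = 55. The 95% half-width is 2.00 × 0.347s = 0.70s, and the 5th to 95th percentile error is 1.645 × 0.347s = 0.57s at every effect size. With 24 subjects, SE = 0.387s on 43 df and the half-width is 0.78s. Using one pair of 10 subjects alone gives 2.26 × √2 × s/√10 = 1.01s.

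**Step 5: a ratio of model-based mean effects.** 30 subjects, 40,000 simulated trials. For a true 1 at 1s/1s, the median estimate is 1.00 (0.52 to 1.91). For a true 2 with a 1s denominator, it is 2.00 (1.32 to 3.8). The Fieller interval covers 95% in every case when always reported. It is bounded in 37%, 90% and 100% of trials at denominator effects of 0.5s, 1s and 2s.

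**The case against.** The best case for the plan has four parts.

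**Other summaries are planned.** SAP 2.1 also gives the median, minimum and maximum, and SAP 2.8.1 lists quartiles for CGM glucose values. An extreme ratio would be visible in these and in listings. This partly stands: at 2s or more the median is reasonable for a true ratio of 1. It does not repair the mean or SD, and the median is biased in the small-effect range where help is most needed.

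**The consequence is small.** The ratio is supplementary, with no test or decision rule. Placebo-adjusted changes for each regimen are reported beside it in glucose units. This stands, and it limits the severity.

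**The table shells and randomization plan are separate files** (SAP 4.3 and 2.12). Ratio direction, allocation or a handling rule might be there. That cannot be excluded, but a mean and SD of individual ratios are what the SAP text itself commits to.

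**The threshold and remedy can be questioned.** At 3s the mean ratio is still poor, and for a true ratio of 2 with a 3s denominator it runs from about -0.1 to 5.2. So 3s is the optimistic end of the threshold, which makes the problem somewhat larger. A narrower fix would keep the ratio and report only its median and IQR. That leaves the bias toward 0.5. A difference is an absolute rather than a relative measure, and that is a real change of quantity.

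**Conclusion.** The concern holds. The mean and SD of the individual ratios are not dependable estimates of dose-response magnitude unless the denominator effect is roughly 3 to 4 or more times the per-period SD of the change. Nothing in either document supports an effect of that size. If the ratios are also formed for the follow-up days, when all subjects are on placebo, any fading of effect makes the denominators smaller still.

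Severity is low to moderate. The problem does not touch the ANOVA or the per-regimen summaries. The figures rest on assumed independent normal periods, equal SDs and an equal split across pairs. Other choices would change the numbers, but not the instability caused by denominators near zero. If effects exceed about 4s, the problem largely disappears.

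**What to change.** In SAP 2.8.1, Protocol 8.3 and the Synopsis, replace the individual ratios as the estimate of dose-response magnitude. Use the differences bid - qd, tid - qd and tid - bid in mg/dL with 95% CIs. Take them from a within-subject model of the change from run-in with subject, period and treatment, using all subjects and all available periods.

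If a ratio is still wanted, state its direction in the SAP text in advance. Report the ratio of regimen-level mean effects from that model with a Fieller interval, in every case, including when the interval is unbounded.

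The cost is wording in three places and a little programming on data already collected. There are four drawbacks:
- The result is in glucose units rather than a unitless ratio.
- The model assumes additive period effects and no carryover.
- Precision remains modest, at about ±0.70s with 30 subjects and ±0.78s with 24.
- A Fieller interval would be unbounded in about 10% of trials at a denominator effect of 1s and about 63% at 0.5s. That is a fair signal that the data cannot support a ratio.
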